3.4.1 Screening

Patient eligibility for the study will be determined within 4 weeks prior to study.

3.4.2 *Treatment*

For each patient, minimum treatment duration is 6 months and a maximum of 52 weeks.

All patients enrolled will be randomized to a minimum of 6 months of treatment in 1 of 4 treatment cohorts. On completion of the 6 months, patients will continue treatment within the same randomized cohort until the last patient reaches 6 months of exposure (for continuing safety assessments), with a maximal exposure period of 12 months. The End of Treatment visits for all patients on treatment will be scheduled no later than the End of Treatment visit of the last patient to complete 6 months of exposure.

The End of Treatment visit should be scheduled one dosing interval post last dose of study drug: one week post last dose for weekly dosing (Cohort D), 2 weeks post last dose for every 2-week dosing (Cohort C), and 4 weeks post last dose for every 4-week dosing (Cohorts A-B). The procedures scheduled for the Week 53/ET visit ([Appendix A](#)) will be performed at the End of Treatment visit. Following the End of Treatment visit patients will then enter a 13-week post-treatment follow-up period.

Eligible patients will report to the Study Center for assessments at specified intervals throughout the 52-week treatment period as detailed in the Schedule of Procedures in [Appendix A](#). During the Treatment, Study Drug (ISIS 678354 or placebo) will be administered by SC injection once-weekly, every 2 weeks, or every 4 weeks, depending on cohort assignment.

3.4.3 *Post-Treatment*

Patients, when completed dosing, will enter the 13-week post-treatment follow-up period and will return to the Study Center for 3 follow-up visits at 4, 8, and 13 weeks post End of Treatment period as per [Appendix A](#) (Follow-up).

The final study visit for each patient will be 13 weeks post End of Treatment period. End of Treatment period is defined as one dosing interval post last dose.

3.5 *End-of-Study*

The End-of-Study is defined as last patient, last visit.

For individual patients, End-of-Study is defined as completion of their last study visit.

3.6 *Data and Safety Monitoring Board*

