8.8 Discontinuation of Study Drug

A patient must permanently discontinue study treatment for any of the following:

- The patient becomes pregnant. Report the pregnancy according to instructions in [Section 9.5.4](#)
- The patient withdraws consent
- The patient experiences an AE that necessitates permanent discontinuation of Study Drug
- The patient develops laboratory test abnormalities that meet any of the stopping rules listed in [Sections 8.6.1](#) to [8.6.4](#)
- When a platelet count of less than 50,000/mm³, or a platelet count less than 75,000/mm³ while the patient is on a reduced dose.

The reason for discontinuation of Study Drug must be recorded in the electronic Case Report Form (eCRF) and source documentation.

8.8.1 *Follow-up Visits for Early Termination from Treatment Period or from Post-Treatment Follow-up Period*

Any patient who discontinues early from the treatment period or from the post-treatment follow-up period should be strongly encouraged to complete follow-up study visits, procedures and observations as described below.

Any patient who discontinues early from the treatment period or from post-treatment follow-up period should be followed as per the platelet monitoring rules shown in [Table 3, Section 8.6.3](#) for the first 6 weeks post end of treatment period and then at 8 and 13 weeks post end of treatment period (as per visit schedule).

If a patient early terminates from the treatment period, an ET visit (Week 53 visit assessments) should be performed at the time of withdrawal, and ideally within 2 weeks from the last dose of Study Drug, and patients should start the 13-week post-treatment follow-up period to collect the study assessments in accordance with the Schedule of Procedures in [Appendix A](#).

If the patient early terminates from the post-treatment follow-up period, a final visit (assessments from the Week 13 of post-treatment follow-up period) should be performed at the time of withdrawal.

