Appendix A Schedule of Procedures – Weekly and Every 2-Week Dosing

	Screening		Treatment Period																			Follow-up Period		
	Run-in [#]	Qual [*]	1	1	5	9	13	17	21	25		26	27 ^q	29	33	37	41	45	49	53/ET	4**	8**	13**	
Study Week	-4 to -2	-2 to -1	1	1	5	9	13	17	21	25	26	27 ^q	29	33	37	41	45	49	53/ET	4**	8**	13**		
Study Day	-28 to -15	-14 to -7	1	2 ^a	29	57	85	113	141	169	170 ^a	171 ^a	176 ^a	183	197	225	253	281	309	337	365	**Weeks from the end of treatment period ^b		
Visit and Testing Window +/- Days	0	0	-3 ^b	0	2	2	2	3	3	3	0	0		3	3	3	3	3	3	3	3	3	3	3
Informed Consent	X																							
Outpatient Visit	X	X	X	X	X	X	X	X	X	X	X	X	X	X	X	X	X	X	X	X	X	X	X	
Inclusion/Exclusion Criteria	X	X	X																					
Medical History ^c	X																							
Vital Signs	X	X	X		X	X	X	X	X															
Physical Examination	X		X		X		X		X															
Body Weight and Height ^d	X	X																						X
12- lead ECG (triplicate)	X		X ¹	X ²	X		X		X	X ¹	X ²	X	X	X										
Extended Urinalysis ^e	X		EVERY 14 DAYS (+/- 2 days) ^f				X	X	X					X	X	X	X	X	X	X	X	X	X	
Renal Biomarkers ^g	X		EVERY 14 DAYS (+/- 2 days) ^f				X	X	X					X	X	X	X	X	X	X	X	X	X	
Serum Creatinine and Cys-C ^{i,j}	X		EVERY 14 DAYS (+/- 2 days) ^f				X	X	X					X	X	X	X	X	X	X	X	X	X	
Chemistry Panel ^{j,k}	X		EVERY 14 DAYS (+/- 2 days) ^f				X	X	X					X	X	X	X	X	X	X	X	X	X	
Hematology ^{j,k}	X	X	HEMATOLOGY PERFORMED EVERY 14 DAYS (+/- 2 days) ^{f,k}																			X ^h	X ^h	X ^h
Coagulation	X		X											X										

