The End of Treatment (EoT) visit for all patients should be scheduled no later than the EoT visit of the last patient to reach 6 months of exposure. The EoT visit should be scheduled to occur at one dosing interval post last dose of Study Drug: one week post last dose for weekly treatment (Cohort D), 2 weeks post last dose for every 2-week treatment (Cohort C), and 4 weeks post last dose for every 4-week treatment (Cohorts A-B). For any patient whose EoT visit would occur later than the EoT visit for the last patient to reach 6 months of exposure, the primary endpoint visit (Week 25 or Week 27 depending on Cohort) will count as the EoT visit.

- **Post-Treatment Follow-up Period:** After the EoT visit has been completed, patients will enter the 13-week post-treatment follow-up period and will return to the Study Center for 3 follow-up visits at 4, 8, and 13 weeks post EoT visit.

1.2 *Objectives*

1.2.1 *Primary Objective*

To evaluate the safety, including tolerability, of ISIS 678354 and to assess the efficacy of different doses and dosing regimens of ISIS 678354 for reduction of serum triglyceride levels in patients with hypertriglyceridemia and established CVD or at a high risk for CVD.

1.2.2 *Secondary Objectives*

To evaluate the efficacy of ISIS 678354 on serum levels of apolipoprotein C-3 (apoC-III), total cholesterol (TC), low density lipoprotein cholesterol (LDL-C), high density lipoprotein cholesterol (HDL-C), non-high density lipoprotein cholesterol (non-HDL-C), very low density lipoprotein cholesterol (VLDL-C), apolipoprotein B100 (apoB) and apolipoprotein A-1 (apoA-I).

To evaluate pharmacokinetics (PK) of ISIS 678354 across different doses and dose regimens in patients with hypertriglyceridemia and established CVD or at a high risk for CVD.

1.2.3 *Exploratory Objectives*

To evaluate the efficacy of ISIS 678354 on serum levels of lipoprotein(a) [Lp(a)], remnant cholesterol, and angiopoietin-like 3 (ANGPTL3).

1.3 *Hypotheses*

The study hypothesis is that ISIS 678354 can significantly reduce the serum triglyceride levels and is well-tolerated for patients with established CVD or at a high risk for CVD.

1.4 *Endpoints*

The primary analysis time point (PAT) is at Week 25 for patients who received every 4-week dosing (Cohorts A and B) and at Week 27 for patients who received weekly or biweekly dosing (Cohorts C

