3.7 Safety Analyses

All safety analyses will use the Safety Set unless otherwise specified. Unless noted otherwise, denominators for all tables will be number of patients in the SS. Safety endpoints including laboratory assessments and vital signs will be analyzed by nominal visit collected on CRF.

Adverse events, concomitant medications, safety shift tables, and all tables related to safety monitoring/stopping rules will be summarized by 2 periods: on-treatment and on-study. On-treatment assessment is defined as the assessment from the first dose to the last dose of Study Drug plus one dosing interval. For Cohorts A and B, on-treatment period spans time from first dose to the last dose + 28 days; For Cohort C, on-treatment period spans time from first dose to the last dose + 14 days;

For Cohort D, on-treatment period spans time from first dose to the last dose + 7 days. On-study assessment is defined as the assessment from the first dose to the last visit in post-treatment follow-up period.

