A confirmed laboratory value is based on consecutive lab values performed on a different day to, but within 7 days (no matter central lab data or local lab data). If consecutive value is same or worse, then the initial value is confirmed. If the consecutive value is better, then the initial value is confirmed using consecutive value. If there is no retest within 7 days, then the initial value is presumed

confirmed. If there are multiple results on the same day (no matter central lab data or local lab data), then the worst value will be utilized in the analysis.

The following lab results will be graded based on Toxicity Grading Scale for Healthy Adult and Adolescent Volunteers Enrolled in Preventive Vaccine Clinical Trials (September 2007). Number and proportion of patients with shift from baseline to worst post-baseline values by toxicity grade will be tabulated for on-treatment and on-study periods. Post-baseline lab results are defined as any assessment taken after the first dose no matter central lab or local lab data. If a patient has no baseline value but has a post-baseline value, then the baseline assessment will be labeled as “unknown”. Likewise, if a patient has a baseline value but has no post-baseline value, then the worst value will be labeled as “unknown”. Shift tables for eGFR, ALT, AST and total bilirubin will be provided using original and confirmed values.

- Hemoglobin: shift from Baseline to minimum post-baseline value
- WBCs: shift from Baseline to minimum post-baseline value
- Platelets: shift from Baseline to minimum post-baseline value
- BUN: shift from Baseline to maximum post baseline value
- Creatinine: shift from Baseline to maximum post-baseline value
- eGFR: shift from Baseline to minimum post-baseline value
- Proteinuria: shift from Baseline to worst post-baseline value
- ALT: shift from Baseline to maximum post-baseline value
- AST: shift from Baseline to maximum post-baseline value
- Alkaline phosphatase: shift from Baseline to maximum post-baseline value
- Total bilirubin: shift from Baseline to maximum post-baseline value

eGFR will be graded using the following criteria:

- $\geq 90 \text{ mL/min}/1.73\text{m}^2$
- $\geq 60 \text{ mL/min}/1.73\text{m}^2$ to $< 90 \text{ mL/min}/1.73\text{m}^2$
- $\geq 30 \text{ mL/min}/1.73\text{m}^2$ to $< 60 \text{ mL/min}/1.73\text{m}^2$
- $\geq 15 \text{ mL/min}/1.73\text{m}^2$ to $< 30 \text{ mL/min}/1.73\text{m}^2$
- $< 15 \text{ mL/min}/1.73\text{m}^2$

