The number and percent of patients who stopped treatment because they met a protocol-defined safety monitoring rule(s) and stopping rule(s) (see Protocol Section 8.6 for details) will be tabulated by treatment group. A listing will be provided for patients who met protocol-defined safety monitoring rules and for patients who terminated treatment due to a protocol-defined stopping rule as well.

Additional investigation of abnormalities in liver chemistry, platelet counts, and renal functions will be performed for on-treatment and on-study periods as below.

Abnormalities in liver chemistry: The number and percent of patients falling in each of the following categories (using available central and local laboratory assessments) will be tabulated based on worst post-baseline assessments by treatment group and for pooled ISIS 678354.

- The higher of ALT > 3 x upper limit of normality (ULN) or ALT > 2 x Baseline
- ALT/AST > 3 x ULN
- ALT/AST > 5 x ULN
- ALT/AST > 8 x ULN
- ALT > 3 x ULN - ≤ 5 x ULN
- ALT > 5 x ULN - ≤ 8 x ULN
- Total bilirubin > 2 x ULN
- ALP > 2 x ULN and (baseline ALP < 2 x ULN or baseline ALP missing)

The number and percent of patients falling in each of the following categories based on confirmed worst post-baseline assessments will be tabulated by treatment group and for pooled ISIS 678354.

- ALT/AST > 8 x ULN, which is confirmed
- ALT/AST > 5 x ULN, which is confirmed and persist for at least 2 weeks
- ALT/AST > 3 x ULN (or the greater of 2 x Baseline value or 3 x ULN if the Baseline value was > ULN), which is confirmed and either:
 - Total bilirubin > 2 x ULN, or
 - INR > 1.5, or
 - Temporal association with symptoms of fatigue, nausea, vomiting, right upper quadrant pain or tenderness (PT: abdominal pain or abdominal pain upper), fever, rash, or eosinophilia (PT: Eosinophilia and the corresponding lab value >ULN within the interval of associated Eosinophilia start and end date); and where temporal will be defined as the report date of the confirmed laboratory parameter occurring within the interval of the associated adverse event start and stop dates

For patients having confirmed 3-fold or greater elevations above the ULN for ALT or AST, a listing of all ALT, AST, total bilirubin, INR, and alkaline phosphatase records will be provided.

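### SAP 3.7 ends the on-treatment period on the target day of the End of Treatment visit, so permitted late samples from that visit drop out of the on-treatment safety tables

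*Combined protocol and SAP*

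**What the plan says.** SAP 3.7 reports adverse events, concomitant medications, shift tables and all monitoring- and stopping-rule tables by two periods, on-treatment and on-study. Its definition is: "On-treatment assessment is defined as the assessment from the first dose to the last dose of Study Drug plus one dosing interval". It then gives the cut-off by cohort: 28 days after the last dose for A and B, 14 days for C, and for the weekly cohort "For Cohort D, on-treatment period spans time from first dose to the last dose + 7 days". On-study runs from first dose to the last follow-up visit.

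Protocol 3.4.2 places the final treatment visit on the same day: "The End of Treatment visit should be scheduled one dosing interval post last dose of study drug". SAP 1.1 repeats this and adds: "After the EoT visit has been completed, patients will enter the 13-week post-treatment follow-up period". In the Appendix A row "Visit and Testing Window +/- Days", both dosing schedules show 3 days at Week 53/ET and also at Week 25 (A/B) and Week 27 (C/D). Those earlier visits count as EoT for some patients.

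SAP 3.7.4 uses the two periods for worst-value laboratory tables: "Number and proportion of patients with shift from baseline to worst post-baseline values by toxicity grade will be tabulated for on-treatment and on-study periods". For organ-specific tables it says: "Additional investigation of abnormalities in liver chemistry, platelet counts, and renal functions will be performed for on-treatment and on-study periods as below". By-visit laboratory summaries use the nominal visit and are not split by period.

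**The concern.** The cut-off is a calendar date with no allowance for the visit window, and it coincides with the visit's target day. A patient seen one to three days late is within the protocol, yet no SAP sentence assigns that visit's laboratory samples to the on-treatment period.

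The period-split laboratory tables rest on the worst post-baseline value, so losing one sample can move a patient into a milder category. With about 20 active patients per group, one patient is 5 percentage points. Protocol 10.1.4 names the incidence of platelet reductions among the dose-selection considerations, though it does not say which table supplies that figure.

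The gap is most visible for chemistry in Cohorts A and B. Samples at dosing visits are drawn before the dose, so the EoT visit is the first scheduled chemistry after the final injection.

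**Working it through.** **Inputs.** Last scheduled doses are from Appendix A: Day 337 (A/B), 351 (C) and 358 (D). Intervals are from SAP 3.7: 28, 14 and 7 days. The EoT target is Day 365 at full length. The window is 3 days either side, read by column position in the Appendix A tables.

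**Reproducing the schedule's EoT day, then comparing it with the permitted range.** Cut-off = last dose day + interval; latest permitted visit = target + 3.

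| Case | Last dose + interval = cut-off | EoT target | Latest permitted | Days in protocol but outside the period |
|---|---|---|---|---|
| A/B, full length | 337 + 28 = 365 | 365 | 368 | 366–368 |
| C, full length | 351 + 14 = 365 | 365 | 368 | 366–368 |
| D, full length | 358 + 7 = 365 | 365 | 368 | 366–368 |
| A/B, EoT at Week 25 | 141 + 28 = 169 | 169 | 172 | 170–172 |
| C, EoT at Week 27 | 169 + 14 = 183 | 183 | 186 | 184–186 |
| D, EoT at Week 27 | 176 + 7 = 183 | 183 | 186 | 184–186 |

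In every case the cut-off equals the target, and 3 of the 7 permitted days (3/7 = 43%) lie beyond it.

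**Chemistry after the final dose.** In A/B at full length, the last dosing visit is Week 49 (Day 337), with chemistry drawn pre-dose; the next scheduled chemistry is Week 53 (Day 365). If that visit is late, no scheduled on-treatment chemistry follows the final dose. The Week 21 and Week 25 visits give the same result at six months. Hematology continues every 14 days, so platelets do not have the same gap.

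**Size.** Visit timing is not given, so this is a range. Active patients per group: 25 × 4/5 = 20. If no visit is late, nothing changes. I assume 10% late as a low figure and 43% (visits spread evenly over the 7 days) as a high one. EoT samples outside the period are then 20 × 0.10 = 2 to 20 × 3/7 = 8.57 per group.

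Suppose each post-baseline sample is equally likely to be the worst. The expected number of changed on-treatment worst values is then the samples excluded divided by the samples per patient. Platelets every 14 days give 12 samples to Day 169 and 26 to Day 365. Chemistry every 14 days to Day 85 and every 4 weeks after that gives 6 + 3 = 9 and 6 + 10 = 16.

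| EoT timing | Test | Samples | 10% late | 43% late |
|---|---|---|---|---|
| Day 365 | Platelets | 26 | 2/26 = 0.08 | 8.57/26 = 0.33 |
| Day 365 | Chemistry | 16 | 2/16 = 0.13 | 8.57/16 = 0.54 |
| Day 169 | Platelets | 12 | 2/12 = 0.17 | 8.57/12 = 0.71 |
| Day 169 | Chemistry | 9 | 2/9 = 0.22 | 8.57/9 = 0.95 |

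The Day 169 rows are ceilings: they need every patient in the group to have EoT at Week 25. Treatment in fact continues until the last patient reaches six months, up to 12 months. Routine hematology has a tighter window of 2 days, so the platelet figures may be slightly high.

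**After the change.** Adding 3 days gives 337 + 31 = 351 + 17 = 358 + 10 = 368 at full length. At six months it gives 141 + 31 = 172, and 169 + 17 = 176 + 10 = 186. No EoT visit within 3 days of its target is then excluded.

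**The case against.** The best defence is that the SAP applies the protocol's own rule. Protocol 6.1.2 defines the treatment period as first to last dose plus one dosing interval, so by that definition a Day 366 sample is post-treatment. This stands: the SAP does not contradict the protocol, and the point is a missing allowance for the visit window.

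Several stronger readings are tempting, but the documents do not support them.

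- **The sample is lost, or belongs to no period.** It is in the on-study period, which SAP 3.7 defines from first dose to the last follow-up visit. It is also in the nominal-visit summaries and the listings.
- **The SAP treats lipids and safety labs from one visit inconsistently.** SAP Appendix A gives lipids a Week 53 window (Days 352 to 379), but that maps efficacy records to visits and does not classify them as on or off treatment. Safety labs from the same visit are also summarized by nominal visit.
- **Early termination in Cohort D is an error.** Protocol 8.8.1 asks for the ET visit "ideally within 2 weeks from the last dose of Study Drug". A sample on days 8 to 14 counts as on-treatment in A, B and C but not in D. That follows from any interval-based cut-off, and the two-week target is guidance on scheduling. A separate 14-day rule would be a preference.
- **Persisting drug effect proves the samples are on-treatment.** The effects lasting at least 4 weeks in protocol 2.3.4 are reported with the lipid results. Taken as the test, they would justify far more than 3 days.

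The cut-off also follows the actual last dose. Against a fixed Day 365 visit, a late final dose narrows the gap (a Day 340 dose in A/B moves the cut-off to Day 368) and an early one widens it. The listed days therefore assume dosing on schedule.

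**Conclusion.** The point holds as a minor one. With doses on schedule, a protocol-compliant EoT visit one to three days after target falls outside the on-treatment period in every cohort. Its samples are then missing from the on-treatment shift, stopping-rule, liver, platelet and renal tables. In Cohorts A and B that can leave no scheduled on-treatment chemistry after the final dose.

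The number of patients affected cannot be derived from the documents. Under the stated assumptions it is probably well under one changed worst value per 20-patient active group. A change shows in a table only if a category boundary is crossed. The primary, secondary and by-visit results do not change. The on-study tables keep the sample, but combine it with 13 weeks of follow-up off drug, so they do not fully replace the on-treatment view.

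**What to change.** In SAP 3.7, end the on-treatment period at last dose plus one dosing interval plus the 3-day visit window: 31 days (A/B), 17 days (C) and 10 days (D). Apply it to all period-split tables: laboratory, adverse event and concomitant medication. Extending laboratory data alone could put a low platelet count and the adverse event it prompted into different periods. State that the analysis period is up to 3 days longer than the treatment period in protocol 6.1.2, and why.

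The cost is one or two sentences and changed constants in the period derivation. No protocol amendment or new data are needed, and dosing, follow-up, the PPS and the efficacy analyses are untouched. The downside is that up to 3 extra days of events, medications and samples count as on-treatment. An EoT visit delayed beyond 3 days, or timed to the calendar after an early final dose, could still fall outside.

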3.7.1 Imputation of Missing/Partial Dates

3.7.1.1 Adverse Events

For AEs, the following imputation rules will be applied to impute start dates under conservative principles:

- If year, month and day are all missing then assign the date of first dose of Study Drug
- If month and day are missing, and year is:
 - the same as the year of the first dose of Study Drug then assign the month-day of first Study Drug
 - earlier than the year of the first dose of Study Drug then assign December 31
 - after the year of the first dose of Study Drug then assign January 1
- If only day is missing, and month-year is:
 - the same as the month-year of the first dose of Study Drug then assign the day of first Study Drug
 - earlier than the month-year of the first dose of Study Drug then assign the last day of the month
 - after the month-year of the first dose of Study Drug then assign the first day of the month

Imputation will be performed for the end date only if the day or month is missing (i.e., year is present) for a resolved AE as follows:

- If month and day are missing, and year is
 - the same as the year of the last dose of Study Drug then assign the month-day of the last dose of Study Drug
 - otherwise, assign December 31
- If only day is missing, then assign the last day of the month

If the imputed start date is later than the imputed end date, then set the imputed start date to the imputed end date.

Analysis period (on-treatment and on-study) will be assigned by comparing the imputed AE start date with the period start/end date.

3.7.1.2 *Prior/Concomitant Medications*

For prior/concomitant medications, the following imputation rules will be applied to impute start dates under conservative principles:

- If year, month and day are all missing, then assign the date of first dose of Study Drug
- If month and day are missing and year is:
 - earlier than the year of the first dose of Study Drug then assign December 31
 - otherwise, assign January 1
- If only day is missing, and month-year is:
 - earlier than the month-year of the first dose of Study Drug then assign the last day of the month
 - otherwise, assign the first day of the month

Imputation will be performed for the end date only if the day or month is missing (i.e., year is present) for a stopped prior/concomitant medication as follows:

- If month and day are missing, then assign December 31
- If only day is missing, then assign the last day of the month

If the imputed start date is later than the imputed end date, then set the imputed start date to the imputed end date.

Analysis period will be assigned by comparing the imputed medication start/end date with the period start/end date.

3.7.2 *Adverse Events*

All AEs will be coded by the Medical Dictionary for Regulatory Activities (MedDRA) version 20.1. Missing or partial dates will be imputed as outlined in Section 3.7.1.

Treatment-emergent adverse events (TEAEs) are defined as adverse events that occurred after the first dose of Study Drug. If the imputed onset date/time is the same as or after the date/time of the first dose of Study Drug, then the event is treatment emergent. An AE with a completely missing start date will be assumed to be treatment emergent.

In the situation where change in severity (but no change in seriousness) occurs for an AE, study sites are instructed to enter an end date for the original AE and start a new record for the AE with a new severity reported. In the new record, the changed severity is to be recorded and the start date will be set to be the end date of the previous record.

When counting the total number of treatment-emergent events for table display, events reporting an increase in severity will be counted as separate events.

AE summary tables by treatment group and overall will be presented in 2 periods separately: on-treatment and on-study. The frequency of patients with any incidence of AEs and the number of events will be summarized by SOC and PT for:

- TEAEs
- TEAEs related to Study Drug. Related is defined as “Related”, “Possible”, or missing relationship to Study Drug
- TEAEs by severity. At each level of patient summarization, a patient with multiple events is counted only once according to the worst reported severity. Adverse events with missing severity will be categorized as “Missing” for this summary.
- TEAEs related to Study Drug by severity
- Most common TEAEs. Most Common TEAE is defined as treatment-emergent adverse events with an incidence of 10% or more within any treatment groups at PT level.
- Treatment Emergent SAEs
- Treatment Emergent SAEs related to Study Drug
- TEAEs leading to permanent treatment discontinuation
- TEAEs leading to death.

Summary tables will be sorted by decreasing frequency of SOC and then by decreasing frequency of PT within SOC in pooled ISIS 678354 group. If the frequency is the same for multiple PTs, sort alphabetically.

An overview of AEs will be provided for all TEAEs. Treatment-emergent AEs, treatment-emergent SAEs, TEAEs related to Study Drug, treatment-emergent SAEs related to Study Drug, TEAEs that lead to Study Drug discontinuation, TEAEs that lead to Study Drug interruption, TEAEs that lead to dose reduction, and TEAEs leading to death will be listed. Note that imputed dates will be used for defining TEAEs and classification of TEAEs into analysis periods.

Listings of all AEs, TEAEs related to Study and Treatment Emergent SAEs related to Study will be presented. Originally reported dates will be used in listings.

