- Definition 2: TEAEs with following PTs or verbatim: influenza like illness, chills, myalgia, arthralgia, pyrexia, feeling hot, or body temperature increased, starting on the day of injection or the next day.

Note that imputed dates will be used for defining.

Treatment Emergent FLRs defined in definition 1 will be summarized by category (i) or (ii). Treatment Emergent FLRs defined in definition 2 will be summarized by SOC and PT. Both definitions will be presented in on-treatment period.

Percentage of injections leading to FLRs (definition 2) for overall and by preferred term will also be summarized using descriptive statistics. Percentage of injections leading to FLRs will be calculated for each patient as $(A/B) * 100$, where A is the number of injections associated with FLRs, and B is the total number of injections.

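### SAP 3.7.1.1 dates a year-only AE end in the last-dose year to the last dose even if the AE began later; the start is then pulled back, so some follow-up AEs count as on-treatment

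*Combined protocol and SAP*

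**What the plan says.** SAP 3.7.1.1 limits end-date imputation as follows: "Imputation will be performed for the end date only if the day or month is missing (i.e., year is present) for a resolved AE". There are three cases:

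- Month and day both missing, year equal to the last-dose year: if the year is "the same as the year of the last dose of Study Drug then assign the month-day of the last dose of Study Drug".
- Month and day both missing, any other year: 31 December.
- Day alone missing: "If only day is missing, then assign the last day of the month".

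A reconciliation rule follows: "If the imputed start date is later than the imputed end date, then set the imputed start date to the imputed end date". The period rule is: "Analysis period (on-treatment and on-study) will be assigned by comparing the imputed AE start date with the period start/end date".

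SAP 3.7.2 confirms the use of these dates: "Note that imputed dates will be used for defining TEAEs and classification of TEAEs into analysis periods". Listings show the originally reported dates.

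SAP 3.7 sets the on-treatment window: "For Cohorts A and B, on-treatment period spans time from first dose to the last dose + 28 days". The extension is 14 days for Cohort C and 7 days for Cohort D. SAP 3.7.2.2 ties both flu-like reaction definitions to onset on an injection day or the day after, and adds: "Note that imputed dates will be used for defining".

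**The concern.** Each rule is ordinary alone; the trouble is the sequence. The end-date rule takes no account of when the event began. If it began after the last dose, the imputed end precedes the start. The reconciliation rule settles that conflict by discarding the start, which is the better-known date, in favour of an end that was only assumed. The resulting start is the last-dose date, which is an injection day and always inside the on-treatment window.

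The trigger can occur. Protocol 9.4.2 records non-serious events to the end of follow-up. SAP 1.1 runs follow-up for 13 weeks after an end-of-treatment visit placed one dosing interval after the last dose.

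At stake are the on-treatment adverse event tables, including serious and bleeding events, and the flu-like reaction tables with the percentage of injections leading to such reactions. Arms are small, so one misplaced event is visible.

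**Working it through.** The plan states no figure to reproduce. The check applies the rules in order to illustrative dates. The documents give no patient dates, so **all calendar dates below are assumptions**.

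**Inputs.** Window extension after last dose: 28 days (A/B), 14 (C), 7 (D), from SAP 3.7. Follow-up: 13 weeks × 7 = 91 days, from SAP 1.1.

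**Rule sequence for a year-only end in the last-dose year**

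1. End = last-dose date.
2. If start > end, start = end = last-dose date.
3. Since last dose ≤ last dose + extension, the event is on-treatment.

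**Mid-year example, end reported only as 2019, start date complete**

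| Cohort | Last dose | Window ends | Reported start | Start after the rules |
|---|---|---|---|---|
| A/B | 24 Jun 2019 | 22 Jul 2019 | 21 Aug 2019 | 24 Jun 2019, on-treatment |
| C | 24 Jun 2019 | 8 Jul 2019 | 7 Aug 2019 | 24 Jun 2019, on-treatment |
| D | 1 Jul 2019 | 8 Jul 2019 | 7 Aug 2019 | 1 Jul 2019, on-treatment |

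Over every possible onset day in follow-up, 91 of 91 are moved on-treatment in each cohort. The largest pull-back is extension + 91: 28 + 91 = 119 days (A/B), 14 + 91 = 105 (C), 7 + 91 = 98 (D).

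**Start with known month, missing day.** An August 2019 onset is imputed as 1 August under the SAP's own start rule. That is after the last dose, so it too is moved to the last-dose date.

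**Where the rules do no harm**

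- If only the end day is missing, the end is the last day of its month: 0 of 91 onset days move.
- If follow-up crosses the year end, an event with start and end in the new year gets 31 December and is not moved. With a last dose on 18 November 2019, the affected onset days are those between the window's end and 31 December: 15 of 91 (A/B, window ends 16 December), 29 (C, 2 December), 36 (D, 25 November).
- An onset after the last dose but within the extension is on-treatment already, so its period does not change, although its onset is still moved to an injection day.

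**Comparator.** SAP 3.7.1.2 assigns 31 December to a year-only medication end date, with no last-dose step. Used for adverse events, that rule moves 0 of 91 onset days in any cohort.

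**Weight of one event.** About 100 patients in 4 cohorts, randomized 4:1, gives 25 × 4/5 = 20 per active group and 4 × 5 = 20 in pooled placebo. One patient is 1/20 = 5%; the 10% threshold for most common events in SAP 3.7.2 is two patients. In the within-cohort bleeding table (SAP 3.7.2.3), one placebo patient is 1/5 = 20%. These figures apply only if the patient has no other on-treatment event in the same row.

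**The case against.** The strongest reply concerns the words *imputed start date*. SAP 3.7.1 is about missing or partial dates, so a complete reported start is arguably not imputed and is left alone. That reading is possible, and a reader should not infer that the SAP plainly overwrites exact dates. But the period-assignment sentence uses the same term for adverse events in general; read narrowly, it would leave events with complete dates without a period rule. Even on the narrow reading, a complete start falls after its own imputed end, and a start with known month and missing day is still moved.

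Several stronger inferences are tempting and not supported:

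- That resolved events in general end at the last dose. The rule needs month and day both missing and the year equal to the last-dose year.
- That every shifted event changes period. Onsets within last dose + 28, 14 or 7 days were on-treatment already.
- That a lone myalgia or arthralgia becomes a flu-like reaction outright. It meets definition 2 only. Definition 1 needs influenza-like illness, or a fever-type term plus at least two of chills, myalgia and arthralgia.
- That the exact onset is often known for such records. Nothing in the documents says how often.
- That injection-site reactions are inflated in the same way. If imputed dates are used there, start and end share one day, so the two-day persistence condition is normally not met.

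It is also fair that Protocol 12.4 and SAP 2.5.1 and 3.1 provide for edit checks, queries and cleaning before lock. The rules are the same in every arm, and listings keep the reported dates, so a shift can be traced. All of that limits the number of records affected and the damage. It does not make the rules right for the records that remain, and tables would then disagree with listings. Nor does the SAP's appeal to conservative principles settle it: that phrase introduces the start-date imputation rules, whereas here reported information is overridden.

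**Conclusion.** The point holds within its trigger. For a resolved event with a year-only end date in the last-dose year and an onset after the on-treatment window, the rules as written give a wrong on-treatment classification and an artificial injection-day onset. For a start with known month and missing day this holds on any reading, provided the first of that month falls after the last dose. For a complete start it holds if *imputed start date* means the start after imputation, which is how the period rule uses it.

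Treatment-emergent status and on-study counts are unaffected, because the event follows the first dose either way. The documents give no basis for counting affected records; the number is probably small, since each must be a resolved event whose end is still year-only at database lock. The correction is worth making because the error is built into the rules, arms have about 20 patients, and the remedy is cheap.

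**What to change.** Make two changes in SAP 3.7.1.1.

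1. Impute a year-only end date in the last-dose year as the later of the event's start date (reported or imputed) and the last-dose date. Alternatively, use the earlier of 31 December and the last study visit, but never a date before the start.
2. Let the start-later-than-end rule change only the missing parts of a start date, never a reported day, month or year.

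In the A/B example, the first option leaves the start at 21 August 2019 and sets the end to the later of 21 August and 24 June, that is 21 August. The event is then on-study only.

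The cost is an edit to two rules and the matching derivation code. No data collection changes.
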